8.3.3.2 RELATIONSHIP TO STUDY INTERVENTION

All adverse events (AEs) must have their relationship to study intervention assessed by the clinician who examines and evaluates the participant based on temporal relationship and his/her clinical judgment. The degree of certainty about causality will be graded using the categories below. In a clinical trial, the study product must always be suspect.

- **Related** – The AE is known to occur with the study intervention, there is a reasonable possibility that the study intervention caused the AE, or there is a temporal relationship between the study intervention and event. Reasonable possibility means that there is evidence to suggest a causal relationship between the study intervention and the AE.
- **Not Related** – There is not a reasonable possibility that the administration of the study intervention caused the event, there is no temporal relationship between the study intervention and event onset, or an alternate etiology has been established.

8.3.3.3 EXPECTEDNESS

The Principal and Sub-Investigators will be responsible for determining whether an adverse event (AE) is expected or unexpected. An AE will be considered unexpected if the nature, severity, or frequency of the event is not consistent with the risk information previously described for the study intervention.

8.3.4 TIME PERIOD AND FREQUENCY FOR EVENT ASSESSMENT AND FOLLOW-UP

The occurrence of an adverse event (AE) or serious adverse event (SAE) may come to the attention of study personnel during study visits and interviews of a study participant presenting for medical care, or upon review by a study monitor.

All AEs including local and systemic reactions not meeting the criteria for SAEs will be captured on the appropriate case report form (CRF). Information to be collected includes event description, time of onset, clinician's assessment of severity, relationship to study product (assessed only by those with the training and authority to make a diagnosis), and time of resolution/stabilization of the event. All AEs occurring while on study must be documented appropriately regardless of relationship. All AEs will be followed to adequate resolution.

Any medical condition that is present at the time that the participant is screened will be considered as baseline and not reported as an AE.

Changes in the severity of an AE will be documented to allow an assessment of the duration of the event at each level of severity to be performed. AEs characterized as intermittent require documentation of onset and duration of each episode.

The study personnel will record all reportable events with start dates occurring any time after informed consent is obtained until 7 (for non-serious AEs) or 30 days (for SAEs) after the last day of study participation. At each study visit, the investigator will inquire about the occurrence of AE/SAEs since the last visit. Events will be followed for outcome information until resolution or stabilization.

8.3.5 ADVERSE EVENT REPORTING

Investigators will report all unanticipated problems that involve risk or harm to a research participant AND was not anticipated or foreseen (e.g., not described in the consent form) AND is probably or definitely related to or caused by the research to the IRB in the required reporting time frame. The IRB at VCUHS will be notified within 5 business days of receiving notice of the unanticipated problem.

VCU will report all unanticipated problems, defined as problems that involve risk or harm to a research participant AND was not anticipated or foreseen (e.g., not described in the consent form) AND is probably or definitely related to or caused by the research, to the DSMB within 7 calendar days of the being notified of the event.

Investigators will also determine if the serious adverse event is unexpected for Vitamin C. Unexpected for Vitamin C is defined as any event not listed in the Vitamin C package insert. If the investigator determines that any serious and study-related adverse event is unexpected for Vitamin C, the FDA will be notified within 7 calendar days. Such events may also meet the definition of Unanticipated Problems as described below.

Examples of untoward clinical occurrences, or disease-related events (DREs) that are expected in the course of AH include: 1) transient hypoxemia, 2) agitation, 3) delirium or hepatic encephalopathy, 4) nosocomial infections, 5) skin breakdown, 6) gastrointestinal bleeding, 7) acute kidney injury, and 8) worsening of hepatic function. Such events, which are often the focus of prevention efforts as part of usual ICU care, will not be considered reportable adverse events unless the event is considered by the investigator to be associated with the study drug or procedures, or unexpectedly severe or frequent for an individual patient sepsis and AH. Examples of unexpectedly frequent untoward clinical occurrences would be repeated episodes of unexplained hypoxemia. This would be in contrast to an isolated episode of transient hypoxemia (e.g., SpO₂ ~85%), related to positioning or suctioning. This latter event would not be considered unexpected by nature, severity or frequency. These events will be captured in the eCRF.

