8.3 ADVERSE EVENTS AND SERIOUS ADVERSE EVENTS

8.3.1 DEFINITION OF ADVERSE EVENTS (AE)

Adverse event means any untoward medical occurrence associated with the use of an intervention in humans, whether or not considered intervention-related (21 CFR 312.32 (a)).

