9.4.3 SAFETY ANALYSES

Adverse Events

Adverse events will be classified into standard terminology using the Medical Dictionary for Regulatory Activities (MedDRA). Adverse events will be listed by reported verbatim term and MedDRA-preferred term, start and stop date and time, study day, duration, severity, relationship to study drug, and seriousness. Additionally, data may be grouped for analysis by different levels of the MedDRA hierarchy. The incidence of AEs, the incidence of treatment-related AEs, and the severity of AEs will be tabulated by cohort (Vitamin C or placebo). The number and percentage of patients with SAEs and treatment-related SAEs and patients who withdraw due to an AE will be tabulated by cohort (Vitamin C or placebo).

Clinical Laboratory Testing

Clinical laboratory test parameters will be listed for individual patients. Baseline for clinical laboratory parameters will be defined as the last evaluation before the start of the initial dosing with study drug. Summary statistics, including mean absolute change from baseline, will be calculated for each parameter and summarized.

Vital Signs

Vital signs results (systolic and diastolic blood pressure, pulse rate, and body temperature) will be listed for individual patients. Each vital sign measure will be tabulated by evaluation time point. Baseline for vital signs measurements will be defined as the last evaluation before the beginning of the first study drug infusion (Vitamin C or placebo, which will generally be Baseline, pre-dose). Summary statistics, including mean absolute change from baseline, will be determined and tabulated for each measure.

Physical Exams

Physical examination findings at baseline will be listed. Clinically significant changes will be recorded as AEs. Symptoms of interest previously reported with intravenous Vitamin C based on the package insert will be recorded daily, including dizziness, headache, nausea, vomiting, flushing, rash, or diarrhea.

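### Section 8.3.5 lets non-serious disease-related events that meet no exception drop out of the by-arm adverse event tables, in conflict with 8.3.1 and 8.3.4

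*Combined protocol and SAP*

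**What the plan says.** Section 8.3.5 (Adverse Event Reporting) names eight disease-related event types expected in alcoholic hepatitis: transient hypoxemia, agitation, delirium or hepatic encephalopathy, nosocomial infections, skin breakdown, and finally "6) gastrointestinal bleeding, 7) acute kidney injury, and 8) worsening of hepatic function". It says these "will not be considered reportable adverse events unless the event is considered by the investigator to be associated with the study drug", and the sentence goes on: "or procedures, or unexpectedly severe or frequent for an individual patient sepsis and AH". After an example about hypoxemia the section closes with "These events will be captured in the eCRF".

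Section 8.3.1 defines an adverse event as "any untoward medical occurrence associated with the use of an intervention in humans, whether or not considered intervention-related", with no exception for events of the underlying disease. Section 8.3.4 says "All AEs occurring while on study must be documented appropriately regardless of relationship". Later in the same section, however, study staff are told to record reportable events within a stated time window. Section 8.3.6 sends every serious adverse event to the sponsor whether or not it is thought related. It treats serious events that are study endpoints separately and does not mention the 8.3.5 list.

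On analysis, 9.4.3 says "The incidence of AEs, the incidence of treatment-related AEs, and the severity of AEs will be tabulated by cohort". It also tabulates SAEs, treatment-related SAEs and withdrawals due to an AE by arm. It does not mention disease-related events.

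**The concern.** In a population this ill, a clinician judging one patient cannot reliably tell a drug effect from the course of the disease. What can show a drug effect is a difference in frequency between randomized arms, and that needs the events counted in both arms whatever their attributed cause. Section 8.3.5 puts a judgement about cause or unusualness in front of the count, and 9.4.3 does not say whether events stopped at that point come back into the tables.

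Safety and tolerability are Hypothesis 1B. With 20 patients, plain counts by arm are most of the safety evidence the trial will produce. If the listed events are counted incompletely, part of that evidence is lost. Two analysts following the text could also build different AE tables from the same data.

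**Working it through.** The plan gives no figure on this point, so the main check sets the sections side by side.

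**1. Does the exemption reach the AE table?**

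| Section | Effect on a non-serious listed event judged unrelated and unremarkable for the patient |
|---|---|
| 8.3.1 | It is an AE |
| 8.3.4, general rule | Must be documented |
| 8.3.4, time window | Recording is tied to reportable events |
| 8.3.5 | Not reportable |
| 8.3.5, last sentence | Captured in the eCRF, but it is unclear whether this means all eight types or only the hypoxemia example just before it |
| 9.4.3 | AEs tabulated by arm; no rule for this class |

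On one reading the event is in the table and on another it is not. The text does not settle which.

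**2. Do the exceptions bring the events back?** Not reliably. Under 8.3.3.2 a temporal relationship is enough to call an event related, while an established alternative cause is enough to call it not related. A listed event during the infusion can satisfy both, and the disease readily supplies the alternative cause. The severity and frequency exception is judged within one patient, and its example is repeated unexplained hypoxemia. An arm with more patients each having one ordinary episode would not trigger it.

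**3. What else compares these events by arm?**

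| Event type | Other by-arm view |
|---|---|
| Acute kidney injury | Creatinine in MELD (96 h); creatinine and renal replacement in CLIF-SOFA (48, 96, 168 h) |
| Hepatic worsening | MELD, MELD-Na, liver tests, overlaid eDISH plots (8.2) |
| Hepatic encephalopathy | West-Haven grade in CLIF-SOFA |
| Hypoxemia | Oxygenation components of SOFA and CLIF-SOFA |
| GI bleeding, nosocomial infection, agitation/delirium, skin breakdown | No dedicated endpoint |

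The scored measures stop at hour 168. The schedule of activities collects creatinine and dialysis at day 28, but no listed endpoint uses them.

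**4. Illustration of size.** The only input from the plan is 10 patients per arm (9.2). The event rates and the share f of events that enter the AE table are assumptions, because the documents give neither. Take one listed event type with rates of 30% on placebo and 60% on vitamin C.

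- Expected patients in the table = 10 × rate × f
- Chance that no vitamin C patient appears = (1 − 0.6f)^10
- Power is for a two-sided Fisher exact test at 0.05, by full enumeration

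| f | Expected, placebo vs vitamin C | No vitamin C patient appears | Power |
|---|---|---|---|
| 1 | 3.0 vs 6.0 | 0.40^10 < 0.001 | 12% |
| 0.5 | 1.5 vs 3.0 | 0.70^10 = 0.03 | 3% |
| 0.25 | 0.75 vs 1.5 | 0.85^10 = 0.20 | 0.5% |
| 0.10 | 0.3 vs 0.6 | 0.94^10 = 0.54 | about 0 |

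Other assumed rates give the same pattern. For 20% versus 40%, full counts are 2.0 versus 4.0 (power 6%), falling to 0.5 versus 1.0 at f = 0.25. For 20% versus 70%, they are 2.0 versus 7.0 (power 43%), falling to 0.5 versus 1.75.

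**The case against.** The strongest reply is that 8.3.5 concerns reporting to the IRB, the DSMB and the FDA, not recording or analysis. Sections 8.3.1 and 8.3.4 keep all AEs on the case report form, 8.3.5 itself says the events are captured, and 9.4.3 tabulates AEs without restricting them to reportable ones. Serious events go to the sponsor under 8.3.6 and are tabulated by arm. The relatedness definition is wide, so timing alone could bring an event in. MELD, SOFA, CLIF-SOFA and eDISH already compare kidney, liver, encephalopathy and oxygenation by arm, and the DSMB reviews data on each arm at least every four weeks until the last patient completes treatment.

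Much of this stands. It defeats the inference a reader might draw that the safety tables will miss the main harms, or that no analysis compares them. It does not close the gap. The time-window rule in 8.3.4 uses the word reportable for recording, so the reporting-only reading is possible but not secured. Section 8.3.5 does not say that it yields to 8.3.6. The DSMB's data elements are left to a charter (10.1.6). The four event types without a dedicated endpoint depend on the AE tables.

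Events after hour 168 should not be laid wholly at the door of 8.3.5, because the AE/SAE row in the schedule of activities also stops there.

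**Conclusion.** The point holds in a limited form. Sections 8.3.1, 8.3.4 and 8.3.5 are inconsistent, and 9.4.3 does not resolve the inconsistency. Non-serious listed events that meet no exception can therefore be absent from the by-arm AE tables. The effect is clearest for gastrointestinal bleeding, nosocomial infection, agitation or delirium, and skin breakdown, and only partial for kidney, liver and encephalopathy events.

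The plan allows no estimate of how many events would be lost. The illustration rests on assumed rates and an assumed share tabulated, and what it shows is thinner descriptive counts, not the loss of a test that would otherwise have had useful power.

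A reader might infer that a large excess of kidney injury on vitamin C could show as zero in both arms. The documents do not support that. Every case would have to be non-serious, judged unrelated to drug and procedures, and unremarkable for the patient, and the creatinine-based scores would still be compared by arm. It is also wrong to say that only attribution to study drug restores reportability, since study procedures, severity and frequency do so too.

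This should be corrected before analysis, but it does not threaten the primary endpoint.

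**What to change.** 1. In 8.3.5, state that the exemption applies to expedited reporting only, and reconcile it with 8.3.1, 8.3.4 (including its recording window) and 8.3.6. Say explicitly that serious listed events follow 8.3.6.
2. Make clear that the closing sentence of 8.3.5 on eCRF capture covers all eight event types.
3. Add to 9.4.3: *The disease-related events listed in 8.3.5 are tabulated by arm (number and percentage of patients, and severity) regardless of attributed cause, and the table is provided to the DSMB.*

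The cost is one extra table and more complete entry of these events in the eCRF for 20 patients. No change to design, sample size or endpoints is needed.

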8.3.6 SERIOUS ADVERSE EVENT REPORTING

The study clinician will immediately report to the sponsor any serious adverse event, whether or not considered study intervention related, including those listed in the protocol or investigator brochure and must include an assessment of whether there is a reasonable possibility that the study intervention caused the event. Study endpoints that are serious adverse events (e.g., all-cause mortality) must be reported in accordance with the protocol unless there is evidence suggesting a causal relationship between the study intervention and the event (e.g., death from anaphylaxis). In that case, the investigator must immediately report the event to the sponsor.

All serious adverse events (SAEs) will be followed until satisfactory resolution or until the site investigator deems the event to be chronic or the participant is stable. Other supporting documentation of the event may be requested by the Data Coordinating Center (DCC)/study sponsor and should be provided as soon as possible.

The study sponsor will be responsible for notifying the Food and Drug Administration (FDA) of any unexpected fatal or life-threatening suspected adverse reaction as soon as possible, but in no case later than 7 calendar days after the sponsor's initial receipt of the information. In addition, the sponsor must notify FDA and all participating investigators in an Investigational New Drug (IND) safety report of potential serious risks, from clinical trials or any other source, as soon as possible, but in no case later than 15 calendar days after the sponsor determines that the information qualifies for reporting.

8.4 UNANTICIPATED PROBLEMS

8.4.1 DEFINITION OF UNANTICIPATED PROBLEMS (UP)

The Office for Human Research Protections (OHRP) considers unanticipated problems involving risks to participants or others to include, in general, any incident, experience, or outcome that meets **all** of the following criteria from the time of consent to through study hour 168 until resolved, withdrawn from the study, death, or lost to follow up:

- Unexpected in terms of nature, severity, or frequency given (a) the research procedures that are described in the protocol-related documents, such as the Institutional Review Board (IRB)-approved research protocol and informed consent document; and (b) the characteristics of the participant population being studied;
- Related or possibly related to participation in the research (“possibly related” means there is a reasonable possibility that the incident, experience, or outcome may have been caused by the procedures involved in the research); and
- Suggests that the research places participants or others at a greater risk of harm (including physical, psychological, economic, or social harm) than was previously known or recognized.

8.4.2 UNANTICIPATED PROBLEM REPORTING

The investigator will report unanticipated problems (UPs) to the reviewing IRB and to the DCC. The UP report will include the following information:

- Protocol identifying information: protocol title and number, PI's name, and the IRB project number;

- A detailed description of the event, incident, experience, or outcome;
- An explanation of the basis for determining that the event, incident, experience, or outcome represents an UP;
- A description of any changes to the protocol or other corrective actions that have been taken or are proposed in response to the UP.

To satisfy the requirement for prompt reporting, UPs will be reported using the following timeline:

- UPs that are serious adverse events (SAEs) will be reported to the IRB and to the DCC/study sponsor within 48 hours of the investigator becoming aware of the event.
- Any other UP will be reported to the IRB and to the DCC/study sponsor within 5 business days of the investigator becoming aware of the problem.
- All UPs should be reported to appropriate institutional officials (as required by an institution's written reporting procedures), the supporting agency head (or designee), and the Office for Human Research Protections (OHRP) within 5 business days of the IRB's receipt of the report of the problem from the investigator.

9 STATISTICAL CONSIDERATIONS

9.1 STATISTICAL HYPOTHESES

Our null hypothesis (H_0) is that intravenous infusion of vitamin C at 200 mg/kg/day will not result in decrease in MELD score from admission to day 4 when compared to placebo.

Our alternative hypothesis (H_1) is that intravenous infusion of vitamin C at 200 mg/kg/day will significantly reduce MELD scores at day 4 compared with MELD on admission in patients with alcoholic hepatitis and sepsis.

9.2 SAMPLE SIZE DETERMINATION

We anticipate an average MELD of 29 on enrollment, with a standard deviation of 5 points, which is based on previous analysis of VCU patient data with alcoholic hepatitis and sepsis. If we assume an alpha of 0.05 and power of 80%, we will need to enroll 8 patients in each arm in order to detect a 25% decrease in MELD on day 4. Therefore, we will overpower and enroll 10 patients in each arm given uncertainties of power calculation. Changes from baseline to day 4 will also be compared across arms by Wilcoxon test. Power calculations were made with NQuery 4.0.

9.3 POPULATIONS FOR ANALYSES

We will perform the following analyses for the study:

- *Intention-to-Treat (ITT) Analysis Dataset:* all randomized participants
- *Modified Intention-to-Treat Analysis Dataset:* participants who took at least one dose of study intervention and/or have some particular amount of follow-up outcome data
- *Safety Analysis Dataset:* subset of participants for whom safety analyses will be conducted (e.g., participants who took at least one dose of study intervention)
- *Per-Protocol Analysis Dataset:* participants in the full analysis (ITT) set who complied with the protocol sufficiently to ensure that these data would be likely to represent the effects of study intervention and will be the primary analysis for all outcomes

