3 OBJECTIVES AND ENDPOINTS

| OBJECTIVES | ENDPOINTS | JUSTIFICATION FOR ENDPOINTS |
|---|--|---|
| Primary | | |
| Vitamin C infusion will significantly attenuate hepatic dysfunction as measured by the model for end stage liver disease (MELD) score | Change in MELD score at 96 hours as compared to baseline when compared to placebo. | MELD score is an independent positive predictor of mortality in patients with AH. |
| Secondary | | |

| OBJECTIVES | ENDPOINTS | JUSTIFICATION FOR ENDPOINTS |
|--|--|---|
| Vitamin C infusion will be safe and tolerable in patients with severe alcoholic hepatitis . | Documented side effects and serious adverse events at hours 24, 48, 96 when compared with hour zero in high dose ascorbic acid versus placebo. | AscA infusion may cause dry mouth, nausea, vomiting, dizziness, headache, flushing, rash, diarrhea. AscA can be excreted from kidney and lead to crystalluria, so will monitor urine pH via urinalysis. Will also monitor EKGs for QTc changes. |
| Secondary | | |
| Vitamin C infusion will attenuate biomarkers of inflammation (C-Reactive Protein, procalcitonin), vascular injury (Thrombomodulin, Angiopoietin-2), while inducing the onset of a fibrinolytic state (Tissue Factor Pathway Inhibitor) | Modulation of available biomarkers | Changes in these biomarkers may provide mechanistic insight into how vitamin C attenuates inflammation |
| Secondary | | |
| Vitamin C Infusion will improve clinical endpoints in this patient population . | 
Change in SOFA Score and Components at hours 48, 96, 168
 
Change in CLIF-SOFA scores and Components at hour 48, 96, 168 when compared to placebo
 
Change in MELD-Na, MDF, Lille scores at hour 48, 96, 168 when compared to placebo
 
Ascorbate level at hour 0, 48, 96, 168 (When feasible)
 
ICU-free days at day 28
 
All-cause mortality to day 28, 90
 
Hospital-free days at day 90
 | CLIF-SOFA, MDF, MELD, and Lille scores are associated with mortality in alcoholic hepatitis. Ascorbate levels are associated with mortality in sepsis patients in the ICU. AH patients have prolonged hospitalizations and are frequently in the ICU. |

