6 STUDY INTERVENTION

6.1 STUDY INTERVENTION(S) ADMINISTRATION

6.1.1 STUDY INTERVENTION DESCRIPTION

All study drug doses will be administered via central or peripheral line infusion. Should no central or peripheral line be available at scheduled time of infusion, a call should be placed to pharmacy to determine if study drug may be piggybacked into the line that is infusing a different drug. If administering study drug via piggyback is contraindicated, then study drug infusion may be delayed by a maximum of 6 hours. If clinical drug administration schedule is such that study drug will not have an available administration time beyond this delay, a dedicated new line (peripheral or central) should be inserted. Study drug will be blinded using an identical appearing placebo.

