6.1.2 DOSING AND ADMINISTRATION

- 1) **First study drug dose** (L-ascorbic acid or placebo) will be considered “Dose 1” and will be administered within 6 hours of randomization or the earliest available time post any clinically indicated procedure which requires the patient to be off the unit. All doses will be administered in the medicine M9W inpatient unit or ICU. Patients receiving vitamin C will receive 25% of the total daily calculated dosing (200mg/kg/24 hours) and will be infused over 30 minutes for this first dosing.
- 2) **Subsequent doses** which represent 25% of the day’s total dose will be infused every six hours through 96 hours (+/- 3 hours).
 - a) Timing of Dose 2 will be triggered by the physician order for q 6 hour administration and will therefore be listed on the bedside MAR. As such, timing of Dose 2 may be out of the +/- 3 hour window and will not trigger a protocol deviation.
 - b) If for any reason any other maintenance dose is not administered within window, the dose will be skipped and the next scheduled dose will be given and documented in the data collection tool.

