7 STUDY INTERVENTION DISCONTINUATION AND PARTICIPANT DISCONTINUATION/WITHDRAWAL

7.1 DISCONTINUATION OF STUDY INTERVENTION

If subjects do not tolerate the drug due to side effects such as nausea, vomiting, flushing, rash, headache, diarrhea, develops crytalluria on urinalysis, or QTc prolongation >50% baseline, we will reduce the subsequent doses by 50%. If the QTc is greater than 550 msec at any time, the drug will be discontinued.

Loss of indwelling venous/arterial catheter or peripheral intravenous access will also trigger the stopping of Vitamin C infusions but subjects will remain on study. Blood glucose monitoring will continue via the central laboratory for 36 hours after the last infusion via peripheral IV draws or peripheral sticks. Biomarker sampling via peripheral IV and/or peripheral stick is allowable as it occurs only 4 times throughout the study and likely only once (if at all) after the patient has been discharged from the unit and is without a central line.

The study drug will be discontinued if a patient develops a metabolic acidosis unexplained by other etiologies (lactic acidosis secondary to septic shock). Determination of the presence of metabolic acidosis will be made by the clinical care team. Study drug will also be discontinued if primary care team or surrogate decision maker request withdrawal. Data collection will continue on these patients following withdrawal of study drug.

Requests to unblind a patient's study treatment can be made to the study (investigational) pharmacist or clinical care team. Unblinding study treatment should occur only in the case of an emergency when knowledge of the study treatment is essential for subject care to treat a serious adverse event and prevent further harm or death.

If possible, a decision to unblind should be discussed with the Principal Investigator or a sub-Investigator prior to unblinding the study treatment.

If a blind is broken (either intentionally or unintentionally), the circumstances should be documented as to who, what, when, and why and all documentation shall be kept by the study pharmacist.

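### Section 9.3 makes an undefined per-protocol set the primary analysis for all outcomes and does not say where patients with halved, skipped or stopped doses or early discharge belong

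*Combined protocol and SAP*

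**What the plan says.** Section 9.3 lists four datasets: intention-to-treat (ITT, everyone randomised), modified ITT, safety and per-protocol. The per-protocol set consists of "participants in the full analysis (ITT) set who complied with the protocol sufficiently" for their data to be likely to "represent the effects of study intervention and will be the primary analysis for all outcomes". So ITT is defined and will be run, but it does not decide the result.

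Other sections create incomplete exposure by design:

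- **Section 6.1.2**, on late doses after Dose 2: "If for any reason any other maintenance dose is not administered within window, the dose will be skipped".
- **Section 7.1**, for intolerance through "side effects such as nausea, vomiting, flushing, rash, headache, diarrhea", and also for crystalluria or QTc prolongation: "we will reduce the subsequent doses by 50" percent. Study drug stops for QTc above 550 msec, unexplained metabolic acidosis, loss of line access, or a request from the care team or surrogate.
- **Section 8.2**: study drug stops for defined AST, ALT or bilirubin rises.
- **Section 4.4**: treatment ends at hospital discharge, withdrawal or death if that comes before 96 hours.

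On follow-up after study drug is withdrawn, Section 7.1 says "Data collection will continue on these patients following withdrawal of study drug".

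**The concern.** In a randomised, placebo-controlled superiority comparison, the analysis that carries the conclusion should keep the groups that randomisation formed. Here it is a subset chosen on what happened after randomisation, by a rule that is not written down.

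A patient whose dose was halved or stopped as directed has followed the protocol, yet may not represent the effect of the assigned regimen. The two halves of the Section 9.3 definition pull apart for exactly these patients.

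Two features could make exclusions informative:

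- **Difference by arm.** The dose-halving symptoms in Section 7.1 all appear in the Section 3 justification: "AscA infusion may cause dry mouth, nausea, vomiting, dizziness, headache, flushing, rash, diarrhea". Halving could therefore be commoner on vitamin C even though Section 6.1.1 states "Study drug will be blinded using an identical appearing placebo".
- **Link to the endpoint.** A bilirubin rise is a stopping trigger (Section 8.2) and also a term in the MELD formula (Section 9.4.2).

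A missed window or a lost line has no stated tie to MELD. What is at stake is whether the primary result can be reproduced from the same 20 patients, and whether the comparison is still the randomised one.

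**Working it through.** **1. Is membership defined elsewhere?** No. Section 6.4 says how adherence is checked (drug log, medical records, eCRF) but sets no level. Section 10.1.10 defines a deviation as any noncompliance, with no major/minor split and no link to the per-protocol set. Section 6.1.2 says an out-of-window Dose 2 is not a deviation; that covers the timing of one dose only. Nothing classifies halved doses, skipped doses, directed stops or early discharge.

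**2. The plan's own sample size.** Inputs from Section 9.2: mean MELD 29, SD 5, 25% decrease, alpha 0.05, power 80%. The difference is 0.25 × 29 = 7.25. Two-sided normal formula: n = 2 × [5 × (1.960 + 0.842) / 7.25]² = 7.47, so 8 per arm. The plan's figure reproduces; it then enrols 10.

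**3. Power as patients leave the set.** Difference 7.25, SD 5, two-sided t-test, noncentrality 7.25 / (5 × √(2/n)):

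| Per arm | t-test | Normal approximation |
|---|---|---|
| 10 | 86.5% | 90.0% |
| 9 | 82.3% | 86.8% |
| 8 | 76.9% | 82.6% |
| 7 | 70.2% | 77.4% |

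**4. How closely bilirubin ties to MELD.** From the Section 9.4.2 formula, a 3 mg/dl rise from b adds 3.78 × ln((b + 3)/b) points: 2.6 from 3 mg/dl, 1.8 from 5, 1.0 from 10, 0.5 from 20. The link exists but is loose at high bilirubin.

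**5. What selective exclusion could do.** The documents give no exclusion rate and no SD for the 96-hour change (the SD of 5 is for enrolment MELD), so these are assumptions: no true effect, 10 per arm, baseline MELD N(29, 5), change SD 5, and analysis of covariance on baseline with a baseline-change correlation from 0 to −0.5. Results are simulated false positives favouring vitamin C at two-sided 5%; the nominal value is 2.5%.

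Partial dependence, where r is the correlation between exclusion and worsening:

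| Excluded (active / placebo) | r = 0.3 | r = 0.5 | r = 0.7 |
|---|---|---|---|
| 20% / 0% | 3.7–3.9% | 4.7–5.1% | 6.0–6.7% |
| 30% / 16% | 3.1–3.2% | 3.6–3.8% | 4.4–4.7% |
| 20% / 20% | 2.5% | 2.5% | 2.5% |

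Exclusion from the active arm only, but unrelated to outcome (r = 0), also stays at 2.5%.

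Upper bound, with the k worst changes certainly removed from active only: the unadjusted shift is −SD × (sum of the top k normal order-statistic means) / (10 − k), with means 1.539, 1.001 and 0.656.

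- k = 1: −5 × 1.539 / 9 = −0.85 points; false positives 5.4–6.1%.
- k = 2: −5 × 2.540 / 8 = −1.59 points; 9.1–10.6%.
- k = 3: −5 × 3.196 / 7 = −2.28 points; 13.2–15.8%.

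With SD 3 the shifts run from −0.51 to −1.37; with SD 7, from −1.20 to −3.20. Removing the best changes instead gives the mirror image.

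**6. What ITT costs in power.** Take 10 per arm and let a share of active patients receive only part of the 7.25-point effect, keeping SD 5. For example, 20% at half effect gives 7.25 × 0.9 = 6.525. The last column leaves the same share out of both arms.

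| Share affected | ITT, half effect | ITT, no effect | Per-protocol |
|---|---|---|---|
| 10% | 83.0% | 78.8% | 82.3% |
| 20% | 78.8% | 68.9% | 76.9% |
| 30% | 74.1% | 57.4% | 70.2% |

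**The case against.** **No bias is demonstrated.** Bias needs exclusion that differs by arm and also tracks outcome. The side-effect route may differ by arm, but nothing ties it to MELD; the bilirubin route tracks MELD, but nothing makes it differ by arm when there is no effect. Either alone leaves the false-positive rate at 2.5%. This stands. The figures in step 5 show what is possible, not what is expected, and the upper bound is hard to reach in a blinded trial.

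**Small losses are tolerable.** One exclusion per arm keeps power above 80%, and the normal approximation keeps it there at 8 per arm. This also stands: the power loss becomes material at two per arm by the t-test, or three by either method.

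**Following a directed halving or stop is compliance.** That is a fair plain reading of the first half of the definition. The second half, about representing the effect of the intervention, still permits exclusion.

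**An on-treatment question suits a proof-of-concept trial, and ITT is reported anyway.** The choice can be argued, but even then the set needs a rule. The stated aim is efficacy against placebo (Sections 4.2 and 9.1), and reporting ITT second does not stop the undefined set from deciding the result.

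**ITT may lack hour-96 values.** This is valid. The Schedule of Activities marks the hour-96 MELD laboratory tests as standard of care, and no draw after hospital discharge is described. Patients discharged early or who have died may have no value, so the remedy needs a missing-data rule.

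**Conclusion.** The concern holds and should be fixed before unblinding. It rests on the text: Section 9.3 gives primary status for every outcome to a set whose membership cannot be determined from the plan, and the protocol generates several kinds of patient whose place in that set is open. The sample size calculation is not at fault.

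The size and direction of any bias are unknown. The false-positive figures depend on assumed exclusion shares, an assumed dependence on outcome and an assumed change SD; they range from no inflation to roughly 13–16% in the extreme case. The power figures use the protocol's inputs, read as a 7.25-point difference with SD 5 applied to the change. The argument for ITT is a defined set protected by randomisation, not greater power: ITT is ahead if affected patients keep half the effect and behind if they keep none.

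**What to change.** In Section 9.3:

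1. Delete the clause that makes the per-protocol set primary for all outcomes.
2. Make the ITT set primary for MELD and the other efficacy outcomes: all randomised patients, as assigned, using hour-96 MELD whether or not study drug was reduced, skipped or stopped.
3. State that safety and tolerability outcomes, including the need for dose reduction listed in the Synopsis, use the safety set.
4. Keep per-protocol as a sensitivity analysis, with written criteria fixed before unblinding that say how directed stops, halved doses, skipped doses and early discharge are classified.
5. Pre-state how deaths and missing hour-96 MELD values are handled. The method is the sponsor's choice, but without it the ITT analysis is not fully specified.

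The cost is wording in 9.3, a short list of criteria and a missing-data rule. No dose, stopping or other clinical rule changes, and Section 7.1 already continues data collection after study drug is withdrawn. The price is the possible dilution shown in step 6 of the working.
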